2.1. Purpose of the Analyses

These analyses will assess the safety and plasma and intrapulmonary pharmacokinetics (PK) of three 6 g doses of ZTI-01 administered as three 1 h IV infusions.

3. STUDY OBJECTIVES AND ENDPOINTS

3.1. Study Objectives

Safety:

• Determine the safety of multiple doses of ZTI-01 (6 g dose every 8 hours, administered as a 1-hour IV infusion, for a total of 18 g in three doses).

Pharmacokinetic:

• Determine the plasma and intrapulmonary PK (epithelial lining fluid (ELF) and alveolar macrophage (AM) concentrations of ZTI-01) after multiple doses of ZTI-01 (6 g dose every 8 hours, administered as a 1-hour IV infusion, for a total of 18 g in three doses).

3.2. Endpoints

Safety:

- The safety outcome measure will be the occurrence of adverse events (AEs), summary of physical exam findings, vital signs, clinical laboratory tests, and electrocardiogram (ECGs) at any time from the start of study drug administration through the end of subject follow-up.
- All subjects who receive at least one dose of study drug will be included in the safety outcome measure. AEs will be collected from the time of dosing on Day 1 through the telephone follow-up interview on Day 3. Treatment Emergent Adverse Events (TEAEs) will be assessed by severity and relationship to the study drug as determined by the investigator.

Pharmacokinetics:

- The pharmacokinetic outcome measures will be plasma and intrapulmonary concentrations of ZTI-01 by validated bioassays.
- Plasma PK parameters will be derived from the plasma concentration vs. time curves after the third dose of study drug. The parameters include, but are not limited to:
- Maximum measured plasma concentration (C_{max})
- Area under the concentration vs. time curve (AUC₀₋₈ and AUC_{0-inf})
- Time to peak concentration (t_{max})
- Terminal elimination half-life $(t_{1/2})$
- \circ Terminal-phase elimination rate constant (λ_z)
- Volume of distribution (V_d)
- Clearance (CL)

Intrapulmonary PK parameters will be derived from the ratios of drug concentrations in ELF and AMs to simultaneous drug concentrations in plasma for each subject and summarized for each sampling time. The median concentrations of fosfomycin from the BAL sampling times will be used to estimate the AUC₀₋₈ of plasma, ELF, and AM. The ratios of AUC₀₋₈ of ELF-to-plasma and AM-to-plasma will be calculated to determine the percent lung penetration.

3.3. Study Definitions and Derived Variables

3.3.1. Fosfomycin Concentrations in ELF and AM

Concentration of Fosfomycin in ELF

The volume of ELF recovered in the BAL samples will be estimated using the urea dilution method [1]. The estimated concentration of fosfomycin in ELF (Fosfomycin_{ELF}) will be calculated as follows:

 $Fosfomycin_{ELF} = Fosfomycin_{BAL} \times (Urea_{Plasma}/Urea_{BAL})$

Where Fosfomycin_{BAL} is the measured fosfomycin concentration in the BAL sample and Urea_{Plasma} and Urea_{BAL} are the measured concentrations of urea in plasma and BAL fluid, respectively.

3.3.2. Definition of AEs

Adverse Events

ICH E6 defines an AE as any untoward medical occurrence in a patient or clinical investigation subject administered a pharmaceutical product, and that does not necessarily have a causal relationship with this treatment. An AE can therefore be any unfavorable and unintended sign (including a clinically significant laboratory abnormality), symptom, or disease temporally associated with use of the study drug, whether or not it is deemed related to the study drug. The occurrence of an AE may come to the attention of study personnel during study visits and interviews of a study subject presenting for medical care, or upon review by a study monitor.

All AEs including local and systemic reactions not meeting the criteria for serious adverse events (SAEs) will be captured on the appropriate case report form (eCRF). Information to be collected includes event description, time of onset, clinician's assessment of severity, relationship to study drug (assessed only by those with the training and authority to make a diagnosis), outcome, action taken, and time of resolution/stabilization of the AE. All AEs occurring while on study will be documented appropriately regardless of relationship. All AEs will be followed until they adequately resolve or are determined by the PI to be medically stable (stable or improving over two assessments and no further intervention required). Any medical condition that is present at the time that the subject is screened will be considered as a baseline finding and not reported as an AE. However, if its Grade increases at any time during the trial such that it meets the AE definition specified above, it will be recorded as an AE.

All systemic and laboratory AEs will be graded using the Adverse Event Toxicity Grading Scale (See Protocol v6.0 Appendix B). Laboratory toxicity grading will be determined by using these tables as modified for the study to accommodate the reference range of the Central Laboratory and the acceptable ranges used in determining eligibility. If a subject was enrolled in the trial with a laboratory value that is outside the reference range, but within the acceptable range, an AE will be recorded if it otherwise meets the definition of AE in Protocol v6.0 Section 9.3 (occurred after the start of infusion of the first dose of study product) and the on-study value is higher (if initially high) or lower (if initially low) than the screening value.

Treatment Emergent Adverse Event (TEAE)

A TEAE is defined as an AE with an onset or increase in either severity or frequency after study drug administration. Since the reporting period for AEs in this protocol is from the time of dosing on Day 1 through the Telephone Follow-up Interview on Day 3, all recorded AEs are by definition TEAEs.

Severity of Event

All AEs will be assessed by the clinician using the protocol-defined grading system.

Changes in the severity of an AE will be documented to allow an assessment of the duration of the AE at each level of intensity to be performed. AEs characterized as intermittent require documentation of onset and duration of each episode.

Relationship to Study Products:

The clinician's assessment of an AE's relationship to the study drug is part of the documentation process, but it is not a factor in determining what is or is not reported in the trial. If there is any doubt as to whether a clinical observation is an AE, it will be reported. All AEs will have their relationship to the study drug assessed using the terms "related" or "not related." In a clinical trial, the study drug must always be suspect. To help assess relatedness, the following guidelines are used.

- Related: There is a reasonable possibility that the study drug caused the AE. Reasonable possibility means that there is evidence to suggest that the study drug caused the AE.
- Not Related: There is not a reasonable possibility that the study drug caused the AE.

Serious Adverse Events (SAE)

An AE or suspected AE is considered "serious" if, in the view of either the investigator or Sponsor, it results in any of the following outcomes:

- Death,
- a life-threatening AE,
- An adverse event is considered life-threatening if, in the view of either the site principal investigator or sponsor, its occurrence places the patient or subject at immediate risk of death. It does not include an adverse event that, had it occurred in a more severe form, might have caused death.
- inpatient hospitalization or prolongation of existing hospitalization,
- a persistent or significant incapacity or substantial disruption of the ability to conduct normal life functions, or
- a congenital anomaly/birth defect.
- Important medical events that may not result in death, be life-threatening, or require hospitalization may be considered serious when, based upon appropriate medical judgment they may jeopardize the subject and may require medical or surgical intervention to prevent one of the outcomes listed in this definition. Examples of such medical events include allergic bronchospasm requiring intensive treatment in an emergency room or at home, blood dyscrasias or convulsions that do not result in inpatient hospitalization, or the development of drug dependency or drug abuse.

All SAEs will be:

- Assessed for severity and relationship to the study drug and alternate etiology,
- Recorded on the appropriate SAE data collection form and eCRF,
- Followed through resolution,

• Reviewed and evaluated by the Independent Safety Monitor (ISM) (as deemed necessary), Safety Monitoring Committee (SMC) (periodic review unless related), DMID, and IRB.

4. INVESTIGATIONAL PLAN

4.1. Overall Study Design and Plan

This is a Phase 1, open-label, multiple-dose trial conducted at a single center. The treatment period will consist of three 6 g doses of ZTI-01 as a 1 h IV infusion. A total of 30 enrolled subjects will be randomized. Six additional enrolled subjects will act as alternates. An evaluable subject is defined as a subject who receives all doses of ZTI-01, undergoes BAL at the randomized sampling timepoint with BAL return volume adequate for testing, and undergoes at least the one blood sampling timepoint that is concurrent with the assigned BAL sampling timepoint, with blood sampling volume that is adequate for testing. Subjects who initiate the Treatment Phase but are not evaluable will be replaced with an alternate at the sample BAL sampling timepoint.

Each subject will complete Screening, Baseline, Treatment, and Follow-up Phases. A diagram of the overall study design is shown in Figure 1. The Screening Phase will be conducted on an outpatient basis within 30 days of the Baseline Phase. The Baseline Phase will consist of admission to DEPRU on the day before the first dose (Day -1) for pre-dosing assessments. The Treatment Phase (Day 1 to Day 2) will include dosing 6 g of ZTI-01, administered as a 1-hour IV infusion, every 8 hours for a total 18 g in 3 doses, followed by post-treatment safety assessments, and BAL and blood sample collections for PK measurements. Each subject will undergo a single standardized bronchoscopy with BAL after the start of the last IV infusion of ZTI-01. Blood samples for PK measurements will be collected before each dose, up to 8 hours after the start of the first IV infusion of ZTI-01, and up to 12 hours after the start of the third IV infusion.

Subjects will remain in DEPRU during the Treatment Phase and will be discharged at least 12 hours after the start of the third IV infusion (if safety parameters are acceptable to the investigator). Safety assessments will be conducted during the entire Treatment Phase. The Follow-Up Phase will consist of a telephone interview on Day 3 for symptom-driven safety assessments.

4.2. Discussion of Study Design, Including the Choice of Control Groups

As the main focus of this protocol is to evaluate the safety and pharmacokinetics of multiple doses of ZTI-01, there is no control group and all subjects receive the same dose of ZTI-01with the same PK blood collection timepoints. Subjects will be randomized to one of five BAL sampling timepoints with a total of 6 subjects assigned to each BAL sampling time.

4.3. Selection of Study Population

The study population for this trial is 36 healthy male and female adults aged 18-45 years, inclusive, with BMI 18-30 kg/m², inclusive, and body weight >50 kg (110 lbs.). Only subjects who meet all inclusion criteria and no exclusion criteria will be eligible for enrollment into the trial. No exemptions are granted on Inclusion/Exclusion Criteria in DMID-sponsored trials.

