# **PROTOCOL SUMMARY**

Title:	A Phase 1 Safety and Intrapulmonary Pharmacokinetics Study of ZTI- 01 (Intravenous Fosfomycin Disodium) in Healthy Adult Subjects
Phase:	1
Population:	40 healthy male and female adults will be enrolled and randomized (to obtain 30 evaluable subjects) aged 18-45 years, inclusive, with BMI 18-30 kg/m  , inclusive, and body weight >50 kg (110 lbs)
Number of Sites:	1 (Duke Early Phase Research Unit [DEPRU], Durham, NC)
Study Duration:	Approximately 6 months
Subject Participation Duration:	Individual subject participation will be approximately 33 days to include up to 30 days between screening and baseline/enrollment, 2 days treatment (dosing) and 1 day of post-dosing follow-up
Description of Agent or Intervention:	ZTI-01 [intravenous (IV) fosfomycin disodium] packed in a single Type 1 glass vial equivalent to 4 g of fosfomycin and 1.28 g of sodium with inactive ingredient of recrystallized succinic acid.
Objectives:	Safety:
	• Determine the safety of multiple doses of ZTI-01 (6 g dose administered as a 1-hour IV infusion (+10 minute window), every 8 hours, for a total of 18 g in three doses)
	Pharmacokinetic:
	• Determine the plasma and intrapulmonary pharmacokinetics (PK) (epithelial lining fluid, and alveolar macrophage concentrations of fosfomycin) after multiple doses of ZTI-01 (6 g dose administered

DMID/NIAID/NIH

27 August 2020

	as a 1-hour IV infusion (+10 minute window), every 8 hours, for a total of 18 g in three doses)
Outcome Measures:	Safety:
	• The occurrence of adverse events (AEs), summary of physical exam findings, vital signs, clinical laboratory tests, and ECGs (B) at any time from the start of study drug administration through the end of subject follow-up
	Pharmacokinetic:
	• Plasma ZTI-01 concentrations will be measured by a validated LC-MS/MS assay for the blood samples collected during the study (Table 3). PK parameters of ZTI-01 will be estimated from the plasma concentration including maximum measured plasma concentration ( $C_{max}$ ), area under the concentration vs. time curve (AUC 0-8 ), time to peak concentration ( $t_{max}$ ), terminal elimination half-life ( $t_{1/2}$ ), terminal-phase elimination rate constant ( $\lambda_z$ ), volume of distribution (Vd), and clearance (CL).

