- 26. History of infection with SARS-CoV-2 (COVID-19) within 3 months of Baseline (Day -1 to Day 1) or unresolved symptoms of COVID-19.
- 27. Positive test for SARS-CoV-2 (COVID-19) at Screening or Baseline (Day -1 to Day 1) within 72 hours of admission

DMID/NIAID/NIH

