# 5.3. Treatment Assignment Procedures

#### 5.3.1. Randomization Procedures

Subjects will be randomized to a single standardized bronchoscopy with BAL sampling timepoint upon study enrollment using an assignment schedule as follows: 30 subjects will be randomized 1:1:1:1:1 to each of the five BAL sampling timepoints (30 minutes, 75 minutes, 2 hours, 5 hours, or 8 hours after the start of the third IV infusion of ZTI-01). Up to ten (10) subjects will be enrolled as alternates. Alternates will arrive at DEPRU on Day -1 to Day 1 and will adopt the planned BAL sampling timepoint of any other enrolled subject who fails to present for check-in or who fails to meet inclusion/exclusion criteria on Day -1 to Day 1. If all scheduled subjects present for check-in and meet Day -1 to Day 1 inclusion/exclusion criteria, then alternates will not undergo any further study procedures at that time. In that case, alternates may be assigned to a new bronchoscopy time on a future date, alternate status for a future date, or as replacement subjects (see Section 5.3.4).

Subjects will be enrolled online using the enrollment module of AdvantageEDCSM software. The randomization code will be prepared by DCC statisticians and included in the enrollment module for this study. AdvantageEDCSM will assign each subject to a sampling timepoint after the demographic and eligibility data have been entered.

Instructions for use of the enrollment module are included in the AdvantageEDCSM User's Guide. Manual back-up procedures and instructions are provided for use in case the site temporarily loses Internet access or the online enrollment system is unavailable.

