4.4.3. Method of Assigning Subjects to BAL Sampling Timepoint Groups (Randomization)

Subjects will be randomized to a single standardized bronchoscopy with BAL sampling timepoint upon study enrollment using an assignment schedule as follows: 30 subjects will be randomized 1:1:1:1:1 to one of the five BAL sampling timepoints (30 minutes, 75 minutes, 2 hours, 5 hours, or 8 hours after the start of the third IV infusion of ZTI-01). Up to six (6) subjects will be enrolled as alternates. Alternates will arrive at DEPRU on Day -1 to Day 1 and will adopt the planned BAL sampling timepoint of any other enrolled subject who fails to present for check-in or who fails to meet inclusion/exclusion criteria on Day -1 to Day 1. If all

scheduled subjects present for check-in and meet Day -1 to Day 1 inclusion/exclusion criteria, then alternates will not undergo any further study procedures at that time. In that case, alternates may be assigned to a new bronchoscopy time on a future date, alternate status for a future date, or as replacement subjects.

Subjects will be enrolled online using the enrollment module of AdvantageEDCSM software. The randomization code will be prepared by DCC statisticians and included in the enrollment module for this study. AdvantageEDC will assign each subject to a sampling timepoint after the demographic and eligibility data have been entered.

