6.6. Interim Analyses and Data Monitoring

No interim analyses are planned. A safety summary report will be generated for review by the Safety Monitoring Committee (SMC) if a halting rule (see Protocol v6.0 Section 9.5) is met.

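### SAP Table 3 gives a lymphocyte count of 500 to <550 two grades; separately, the SAP still restates 36 subjects and cites protocol v6.0 where protocol v9.0 plans 40

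*SAP*

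**What the plan says.** **Lymphocyte grading.** SAP Table 3 sets lymphocyte decrease at 500 to <600 cells/mm3 for Grade 1, 400 to <550 for Grade 2 and <400 for Grade 3. Protocol Table 11 (Appendix B) has 500 to <600, 400 to <500 and <400. SAP 9.6 makes Table 3 the scale for the laboratory severity summaries. Adverse events are graded by the protocol's Appendix B, according to protocol 9.2.1 and also SAP 3.3.2 ("See Protocol v6.0 Appendix B").

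**Planned size.** SAP 4.3 says "The study population for this trial is 36 healthy male and female adults". SAP 4.1 says "Six additional enrolled subjects will act as alternates", as does SAP Section 2, and SAP 4.4.3 says "Up to six (6) subjects will be enrolled as alternates". The Protocol Summary says "40 healthy male and female adults will be enrolled and randomized (to obtain 30 evaluable subjects", and protocol 5.3.1 says "Up to ten (10) subjects will be enrolled as alternates". Protocol Section 4 also gives ten alternates, and protocol 7.1 and 11.2 also give 40.

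**Versions.** The SAP is marked Version 1.0, 20FEB2020. It cites protocol v6.0 in 3.3.2 and again for the halting rules in 6.6 ("see Protocol v6.0 Section 9.5"). The protocol supplied is Version 9.0, 27 August 2020.

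**Eligibility.** The list in SAP 4.3.2 stops at exclusion criterion 25. Protocol 5.2 continues with 26 (recent or unresolved COVID-19) and 27 ("Positive test for SARS-CoV-2 (COVID-19) at Screening or Baseline").

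**The concern.** The lymphocyte band is wrong as written, because one count falls in two grades. SAP 9.6 sends hematology results to a severity table (Table 22) and a listing of results of Grade 1 or above (Table 17), and Listing 10 prints a grade beside each result. A programmer who codes Table 3 as it stands must choose a rule for 500 to <550, and the plan gives none. If Grade 2 is chosen, Table 22 can disagree with the adverse event tables, where the same count is Grade 1 under Appendix B. It can also show a Grade 2 baseline in a subject who was properly enrolled: criterion 25 excludes Grade 2 by Appendix B but lets the investigator accept a Grade 1 value.

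The planned size and version citations are a different matter. Here the SAP restates design facts that the protocol has since changed. Protocol Section 16 says both documents will be posted with the results, so they would disagree in public on the planned size, the number of alternates and the eligibility list. SAP Section 15 rules out amending the SAP after final data lock, so there is a deadline.

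**Working it through.** **A. Lymphocyte band.** Inputs are the three bands in SAP Table 3 and in protocol Table 11. Grading test values under each gives:

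| Count (cells/mm3) | SAP Table 3 | Protocol Table 11 |
|---|---|---|
| 399 | 3 | 3 |
| 400 | 2 | 2 |
| 499 | 2 | 2 |
| 500 | 1 and 2 | 1 |
| 549 | 1 and 2 | 1 |
| 550 | 1 | 1 |
| 599 | 1 | 1 |

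- The overlap is 550 − 500 = 50 cells/mm3, which is half of the Grade 1 band (600 − 500 = 100).
- Outside 500 to <550 the two tables agree. The Grade 3 limit (<400) is the same in both.
- Halting rules (protocol 9.5): the laboratory rule needs Grade 3 events. The individual rule concerns sodium, potassium, magnesium, calcium and phosphorus. Neither uses a lymphocyte Grade 2.
- Eligibility: SAP 4.3.2 and protocol 5.2 both refer criterion 25 to the protocol's Appendix B, so enrolment decisions do not use SAP Table 3.

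**B. Planned size.**

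1. Randomized, both documents: 5 BAL times × 6 = 30.
2. SAP figure reproduced: 30 + 6 alternates = 36, as SAP 4.3 states.
3. Protocol figure reproduced: 30 + 10 alternates = 40, as the Protocol Summary and 11.2 state.
4. Gap: 40 − 36 = 4 subjects, or 4/40 = 10% of the protocol's number.
5. Enrolled subjects that can be lost with 30 evaluable still reached: 6/36 = 16.7% on the SAP's numbers and 10/40 = 25.0% on the protocol's.

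**C. Does 36 enter any analysis?** SAP Section 5 gives no number and no power calculation. Tables 5 and 6 use the number actually enrolled, shown as N=X. The Safety Population (6.3.1) is everyone who starts an infusion, and the PK Population (6.3.2) is the evaluable subjects. Neither 36 nor 40 enters a denominator or an estimate.

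**The case against.** The best defence of the planned size is that nothing was miscalculated. The SAP predates protocol v9.0 by about six months, its own sum is right, the evaluable target is unchanged, and the protocol governs enrolment and eligibility. SAP Section 15 allows an addendum before lock, and SAP Section 1 requires deviations to be described and justified. All of that stands. It makes this a text correction, but it does not make the text correct.

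For the lymphocyte band, protocol 9.2.1 and SAP 3.3.2 allow the toxicity tables to be modified to suit the laboratory's reference range. That cannot explain the entry: a local change to the top of Grade 2 would have to move the bottom of Grade 1 as well, and it did not move. The other legible laboratory rows match protocol Table 11, which suggests an isolated slip.

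A reader might infer more than the documents support:

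- *That the SAP's 36 lowers the chance of reaching 30 evaluable subjects.* If each subject were independently non-evaluable with an assumed probability of 10%, 15% or 20%, the chance of at least 30 would be 94%, 71% or 40% with 36 dosed, and >99%, 97% or 84% with 40. These rates are not in the documents. Alternates also cover no-shows and baseline failures, so not every enrolled subject is dosed. Above all, a stale sentence in the SAP does not stop enrolment at 36.
- *That the lymphocyte band came from v6.0, or that the halting rules changed between versions.* Protocol v6.0 is not available, so neither can be shown. In v9.0 the halting rules are still in Section 9.5, and the SAP 6.6 citation only triggers a safety report for the SMC.
- *That leaving out the +10 minute infusion window alters the PK results.* SAP 10.2 uses the actual infusion duration.
- *That Table 7 will omit criteria 26 and 27.* Its rows are placeholders.

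**Conclusion.** The point holds in two separate parts.

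1. SAP Table 3 is wrong for lymphocytes. Counts of 500 to <550 carry both Grade 1 and Grade 2, against Grade 1 only in protocol Table 11. The effect is confined to the lymphocyte rows of the hematology severity table and the hematology listings. The documents give no lymphocyte distribution, so the number of results affected cannot be estimated. This is the only item here that can change a reported result.
2. The SAP's restated design is out of date by four enrolled subjects (36 against 40), four alternates (six against ten) and two exclusion criteria, and it cites v6.0 in place of v9.0. This is version lag, not an arithmetic error, and no analysis depends on it.

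A causal link between the two parts might be inferred, but nothing in the documents shows one. The conclusion rests on taking protocol v9.0 as the version in force and SAP v1.0 as the current SAP.

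**What to change.** Before database lock, by SAP amendment or by an addendum under SAP Section 15:

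- Reconcile the Table 3 lymphocyte Grade 2 band with protocol Table 11, the scale by which adverse events are graded, so that each count has one grade.
- In SAP 4.3 restate the planned size as 40, and in Sections 2, 4.1 and 4.4.3 restate the alternates as ten. Word it as 30 randomized plus ten alternates, as in protocol Section 4 and 5.3.1, because the Protocol Summary speaks of all 40 as randomized.
- Add exclusion criteria 26 and 27 to SAP 4.3.2.
- Change the v6.0 citations in SAP 3.3.2 and 6.6 to v9.0, after checking that the cited sections still say what the SAP relies on.

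The cost is an edit to the SAP and one grading limit in the programming specification. It needs no further subjects, samples or analyses beyond those the protocol already plans.
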